Aim 1. Test the feasibility of having participants consume liquid and solid foods for 1 month and demonstrate our ability to acquire and analyze fMRI brain activation pre and post dietary intervention with a visual reward paradigm.

Aim 2. Test for change in body weight.

Hypothesis: The SSB group will have no difference in change in body weight compared to the solid group (between group effects). The SSB and solid groups will have increased weight compared to baseline (within group effects).

Changes in brain activation will be measured and tested for differences among the groups. It is hypothesized that change in brain activity will not differ between the SSB and solid groups. But, it is hypothesized that both the SSB and solid group will experience change in activation in reward-related areas of the brain compared to baseline.

The foods listed above will be provided to participants with instructions to consume one serving per day. The energy content of food provision in the SSB and solid groups will be 240 kcal/day (SSB and solid groups will be isocaloric). Participants will receive no instructions for other dietary modifications; i.e., they will not be told to modify what or how much other food they consume.

Inclusion and Exclusion Criteria:

The target study group will be 20 men and women aged 21 to 65 years. 10 participants will be randomized to the SSB and solid groups, respectively. The participant population will include normal weight, overweight and obese (BMI 20.0 to 40.0 kg/m²) individuals. All inclusion/exclusion criteria will be based upon self-reported medical history/checklist. Participants must be able to consume study foods and be willing to archive their brain scans and eye tracking data. Participants who consume SSBs will be asked to maintain their regular SSB consumption in addition to the SSB (or solid food) associated with their random assignment). Participants will be stratified based on sex and BMI class.

Exclusion Criteria:

Health Conditions:

- Diabetes (Type 1 or 2)
- Prediabetes
- Active cancer
- Serious digestive disorders
- Other conditions that affect metabolism or body weight
- Uncontrolled Thyroid disorder (controlled = 6 months of medication)
- Unable to consume study foods
- Non- weight stable (more than 10 lbs. weight gain or loss in last 6 months)
- Pregnancy
- Intentions of becoming pregnant in the next 2 months
- Women who have undergone partial hysterectomy with intact ovary function

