The Advertising and Recruitment Cores are responsible for recruiting potential participants for clinical trials from a population that includes a wide range of people of various ages, ethnic backgrounds and with varying degrees of health. Pennington Biomedical has a team of full-time employees dedicated to the recruitment and initial screening of clinical trials. Potential subjects will be identified via a large database of previous study participants along with the use of web, print, and media advertising. The Recruitment and Advertising Cores create and implement individualized, trial-specific advertising and awareness campaigns, including mass media, traditional advertising, and novel methods including social media, digital and email marketing. All advertising and awareness are approved by our on-site IRB to ensure ethical and disclosure standards are met. The PBRC database will also be utilized to find potential subjects for this study.

Study Timelines

Participants will come in for a screening visit. Then approximately a week (~ 7 days) later, participants will come in their Week 0 (baseline) study visit and be provided with ~1 week (~7

days) of food provision. This visit will occur based on self-reported luteal phase of menstrual cycle in women. Next, at approximately 1 week (~day 7), participants will return to the center for an adherence visit and further provision of study foods (Week 1). At approximately 2 weeks (~day 14), participants will return to the center for an adherence visit and further provision of study foods (Week 2). At approximately 3 weeks (~day 21), participants will return to the center for an adherence visit and further provision of study foods (Week 3). Finally, participants will come for their Week 4 assessment and adherence visit. Thus, participation will last approximately 5-6 weeks in total.

Study Endpoints

Study Design: A randomized parallel arm design trial examining solid sugar vs. SSB treatments will be performed. The primary study endpoints are feasibility and change in body weight.

Procedures Involved

Overview:

Participants will arrive at the center following a minimum 10 hour fast. They will undergo anthropometric measurements, psychological and behavioral questionnaires, and fMRI.

Table 1. Schedule of Procedures

| Visit Assessments | Screening Visit | Intervention Period | | | | |
|--|-----------------|---------------------|--------|--------|--------|--------|

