| | | Week 0 | Week 1 | Week 2 | Week 3 | Week 4 |
| Informed Consent | X | | | | | |
| Anthropometrics (height, body weight) | X | | | | | |
| Anthropometrics (body weight, waist and hip circumference, and bioelectrical impedance) | | X | | | | X |
| Brief Lifestyle Interview and non-quantified food record | X | | | | | |
| Contact and Demographic Information | X | | | | | |
| Food Taste Test | X | | | | | |
| Food Craving Inventory (FCI), Yale Food Addiction Survey (YFAS) , Liking and Wanting Procedure, Retrospective Visual Analogue Scales (RVAS) , Barratt Impulsiveness Scale, Delayed Discounting Task, and Food Familiarity and Liking Procedure | | X | | | | X |
| Urine Pregnancy Test | | X | | | | X |
| fMRI (fasting and fed state) | | X | | | | X |
| Randomization | | X | | | | |
| Study Product Dispensed | | X | X | X | X | |
| Adherence check/calculations (self-report and container return), provision of study foods | | | X | X | X | X |

Dose: The energy content of food provision in the SSB and solid groups will be 240 kcal/day. Participants are to consume 1 unit per day of the study.

Diet: Participants will receive no instructions for other dietary modifications; i.e., they will not be told to modify what or how much other food they consume.

Food Acceptability Form: Participants will be asked to rate the study foods for appearance, odor, flavor, texture, sweetness, and overall acceptability at screening. Each participant will be asked to circle the number from 1-9 for each of the characteristics after consuming the study foods.

Psychological Assessments:

Food Craving Inventory (FCI). The FCI^{9,10} is a 28-item measure of specific food craving. The FCI assesses the frequency with which an individual experiences a craving for a particular food. The measure consists of 4 empirically-derived factors: High fats, Sweets, Carbohydrates/starches, and Fast food fats. All items are scored in a 1 (Never) to 5 (Always) multiple choice format. The measure has been shown to be reliable and support has been found all aspects of validity.

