- MRI/fMRI – fasting and fed state
- Treatment consumption – fed state fMRI
- 1 week supply of study product dispensed

Week 1: About 30 minutes – Non-Fasting

- Adherence check
- 1 week supply of study product dispensed

Week 2: About 30 minutes – Non-Fasting

- Adherence check
- 1 week supply of study product dispensed

Week 3: About 30 minutes – Non-Fasting

- Adherence check
- 1 week supply of study product dispensed

Week 4: About 4 hours – Fasting (nothing to eat or drink other than water for at least 10 hours prior to visit) after at least 7 hours of rest the previous evening

This visit will take place in the Outpatient Clinic Department of Pennington Biomedical. The testing this day includes the following procedures:

- Anthropometric Measurements – (body weight, waist and hip circumference, and bioelectrical impedance)
- Psychological and Behavioral Questionnaires
- Females of child-bearing potential will have a urine pregnancy test
- MRI/fMRI – fasting and fed state
- Treatment consumption – fed state fMRI
- Adherence check

All participants need to come in within \pm 2 days of their scheduled visit date.

Phone calls, text messages and email are also permissible by the adherence coach as adherence checks during the dietary intervention. Also adherence coaches can request remote motoring i.e. pictures of study foods.

Study Procedures:

As previously stated, the foods listed above will be provided to participants with instructions to consume one serving per day. If they happen to skip a day, participants will be instructed to consume the treatment on the following day on top of their normal daily provision. The energy content of food provision in the SSB and solid groups will be 240 kcal/day (SSB and solid groups will be isocaloric). Participants will receive no instructions for other dietary modifications; i.e., they will not be told to modify what or how much other food they consume.

fMRI: Reward Activation

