At baseline and follow-up, subjects will arrive to PBRC after an overnight fast where they will participate in a fMRI scanning protocol to assess brain response patterns to reaction times and attentional processing to food and control images. The scanning session will begin with a structural scan where the participant will be asked to lie as still as possible while we scan their brain. The paradigm will immediately follow in which subjects will view images of pictures with up to seven categories: 1) High Sugar/High Fat (HS/HF), 2) High Complex Carbohydrate/High Fat (HCC/HF), 3) Low Carbohydrate/High Protein/High Fat (LC/HP/HF), 4) High Sugar/Low Fat (HS/LF), 5) High Complex Carbohydrate/Low Fat (HCC/LF), 6) Low

Carbohydrate/High Protein/ Low Fat (LC/HP/LF), and/or 7) Control Images presented in an event design. Subjects will also be asked to solve a mental task which may include clicking buttons to rate pictures. Additionally, we may collect eye tracking data during the fMRI scanning protocol to further assess attentional processing of food-related visual cues.

Fasting vs. Fed Neural Activation Patterns:

Subjects will complete all scanning procedures in a fasting state and additionally post meal consumption. After completing the fMRI scan in the fasted state, subjects will participate in a meal challenge by consuming their dietary treatment and after will undergo the same fMRI image protocol as before to assess changes in activation in response to fasted and fed conditions. Recently Smeets et al. investigated how neural activation patterns in response to caloric and non-caloric stimuli are modulated by hunger (fasted) and satiety (fed). They showed a significant interaction between hunger and energy content in the solutions and that tasting energy during satiety resulted in greater activation patterns than during hunger¹⁷. For these reasons, we will assess reward activation patterns in response to food cues in the fasted and fed state.

MR scan preparation

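### Does taking the Week 0 fed-state fMRI after the assigned food leave the fed-state change without a valid baseline?

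*Protocol*

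**What the plan says.** Table 1 (Schedule of Procedures) places randomisation at Week 0 and fMRI, fasting and fed, at Weeks 0 and 4. It does not order the steps within the Week 0 visit. The visit lists for Week 0 and Week 4 both include "Treatment consumption – fed state fMRI". The section Fasting vs. Fed Neural Activation Patterns says that, once the fasted scan is done, "subjects will participate in a meal challenge by consuming their dietary treatment and after will undergo the same fMRI image protocol as before". It gives the purpose as assessing how activation differs between the fasted and fed conditions.

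Three other places matter:

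- **Labels.** Study Timelines says "participants will come in their Week 0 (baseline) study visit", and Aim 1 is to "acquire and analyze fMRI brain activation pre and post dietary intervention with a visual reward paradigm".
- **Hypothesis.** Aim 2 says "Changes in brain activation will be measured and tested for differences among the groups". It expects no difference between the arms in change, and a change from baseline within each arm.
- **Analysis.** The Statistical analysis paragraph specifies a mixed model ANOVA for between-group differences in change, and LS Means tests of change from baseline against zero. It names no fed-state outcome and no fMRI contrast.

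Study Endpoints names feasibility and weight change as primary. Power Analysis states that no power calculation was done because this is a pilot.

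**The concern.** A baseline is normally measured before treatment. Here the food eaten before the Week 0 fed scan is the participant's own assigned product, so that scan already carries any acute effect of one serving. Only the Week 0 fasted scan comes before it.

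If the change test is run on the fed scans, an acute difference between the arms that appears at the first serving and stays constant is subtracted from itself. One that fades over the month comes out with a negative sign. The protocol also predicts no difference between arms in change. A null fed-state result would therefore seem to confirm the hypothesis, although it is expected both when food form has no effect and when it has an immediate, lasting one. Food form is what distinguishes these isocaloric arms, so a misread null could carry over into the larger study that this pilot is meant to inform.

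**Working it through.** **Inputs from the protocol.** 20 participants, 10 per arm, two states at each of two visits. At Week 0 that is 20 × 2 = 40 scans: 20 fasted, before the assigned food, and 20 fed, after it. That randomisation comes before the serving is inferred from the reference to each participant's own treatment. The protocol gives no SD, effect size or significance level for fMRI, so there is no figure of its own to reproduce.

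**Definitions (arm differences, SSB minus solid).**
- a0, a4: difference in fed-minus-fasted activation at Week 0 and Week 4.
- g4: difference in fasted activation at Week 4.
- The fasted difference at Week 0 is 0 in expectation, by randomisation.
- Order and retest effects common to both arms cancel.

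**What each contrast estimates.**
- Week 0 fed minus fasted: a0, the acute effect at the first assigned serving.
- Week 4 fed minus fasted: a4, the acute effect after a month.
- Week 4 fasted minus Week 0 fasted: g4.
- Week 4 fed minus Week 0 fed: (a4 + g4) − a0 = g4 + (a4 − a0).
- Week 4 fed minus Week 0 fasted: a4 + g4, the acute and month-long effects together.

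**Numbers put in (assumed, in units of the scan SD).** The fed difference between arms is a0 at Week 0 and a4 + g4 at Week 4.

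| a0 | a4 | g4 | Fed difference, Week 0 | Fed difference, Week 4 | Fed-change contrast |
|---|---|---|---|---|---|
| 1 | 1 | 0 | 1 | 1 | 0 |
| 1 | 0.5 | 0 | 1 | 0.5 | −0.5 |
| 1 | 1.5 | 0 | 1 | 1.5 | +0.5 |
| 1 | 0.5 | 0.5 | 1 | 1 | 0 |

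A simulation (20,000 runs, between-scan correlation 0.5) gave 0.003, −0.504 and −0.004 for the first, second and fourth rows. The cancellation is therefore real. But in every row the contrast equals the actual change in the fed difference from Week 0 to Week 4. The negative sign for a fading effect simply reports that the difference shrank.

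**Does the contrast find what it is meant to find?** In a second simulation (40,000 runs, 10 per arm, SD 1, two-sided 5% level, all assumed):
- Stable acute difference of 1 SD, no later change: fed change estimated at about 0.00, rejected in about 5% of runs. That is the correct result for no change.
- No acute difference, 1 SD arising over the month (correlation 0.5): estimated at 1.0, rejected in about 56% of runs.
- The same stable 1 SD acute difference, examined as Week 0 fed minus fasted: estimated at 1.0, rejected in about 43% to 78% of runs for correlations of 0.3 to 0.7.

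So fed change answers the question about change, and fed minus fasted answers the question about the acute effect. Both come from scans already scheduled.

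**Precision of any one such contrast.** SE = √(2(1 − r)) × √(2/10), which is 0.529, 0.447 and 0.346 for r = 0.3, 0.5 and 0.7. Multiplied by t(18 df) = 2.101, the 95% half-widths are 1.11, 0.94 and 0.73 SD. An acute contrast in this pilot could only be an estimate with a wide interval, whatever the protocol said about it.

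**The texts side by side.** The Background and Aim 1 define the intervention as intake over one month. Study Timelines uses baseline as the name of a visit. Aim 1's before-and-after wording fits the month of food provision. Nowhere is the Week 0 fed scan described as untreated. Participants in both arms also eat the study foods at screening, where they "circle the number from 1-9 for each of the characteristics after consuming the study foods", so the protocol does not treat a single tasting as the intervention.

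**The case for a change.** The strongest case for the concern is that the protocol itself, and not an unseen analysis plan, fixes the baseline label, the before-and-after description and the tests of change from baseline, without a separate rule for fed scans. A reader who applies those tests literally to fed activation gets a contrast blind to a stable acute effect of food form, in a trial about food form. The meal challenge is there to study the fed response, yet no sentence expressly ties the fasted-versus-fed comparison to a comparison between arms.

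The facts and the algebra in this stand. The step to a fault does not. A contrast of change is blind to whatever does not change, and change is what Aim 2 hypothesises about. The protocol states no hypothesis about the acute effect of one serving, so requiring that contrast would add a question to the trial. The Statistical analysis paragraph does not say that fed change is an outcome. The purpose given for the fed scan is the within-visit comparison with the fasted scan, and together with Aim 2's "Changes in brain activation will be measured and tested for differences among the groups" this leaves room for the between-arm version. No sentence says that a null fed change would be read as no effect of food form on fed activation.

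A related point is that change within an arm also contains retest and time effects: an assumed visit shift of 0.3 SD common to both arms gives a fed change of 0.30 in each arm even if neither response to the food has altered. That is true, but it follows from having no untreated arm. It applies equally to the change between fasted scans and does not depend on what was eaten before the Week 0 fed scan.

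**Conclusion.** The concern does not hold. The Week 0 fed scan does follow the assigned food, and a stable acute difference does cancel from Week 4 fed minus Week 0 fed. But repeating the same meal challenge before and after the month is a valid way to measure change in the fed response, and change is what the protocol hypothesises about. No stated rule gives a wrong result and no two passages conflict.

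The order of steps within Week 0, the labelling of fed-state results and the choice of fMRI contrasts are details commonly left to a statistical analysis plan, which may exist and is not shown. Spelling them out would be helpful but optional. Nothing is lost for the primary endpoints or the fasted scans, and the acute contrast can be computed from scans already planned.

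This conclusion rests on reading the intervention as the month of daily intake, as the Background and Aim 1 describe it. The effect sizes, SD, correlations and significance level used in the check are assumptions. The algebra does not depend on them.

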- Any uncorrected vision problems
- Color-blindness
- Left-handed
- Current or past alcohol or drug abuse problem

- Have internal metal medical devices including cardiac pacemakers, aortic or cerebral aneurysm clips, artificial heart valves, ferromagnetic implants, shrapnel, wire sutures, joint replacements, bone or joint pins/rods/screws/clips, metal plates, metal fragments in your eye, or non-removable metal jewelry such as rings.
- Other contraindications to magnetic resonance scanning
- Unable or unwilling to complete the imaging procedures for the duration of the MRI scan due to claustrophobia or other reason.
- Allergy or intolerance to study product ingredients.
- Any other medical, psychiatric or behavioral factors that in the judgment of the Principle Investigator that may interfere with study participation or the ability to follow the protocol

Medications/Non-Drug Therapies (within ~4 weeks prior to Screening):

- Weight loss medications, diet pills
- Non-topical steroids
- Other medications that may affect fluid balance or weight

Lifestyle:

- Consume more than seven 12 oz. sugar-sweetened beverages per week (~ 1, 12 oz. SSB/day; diet soft drinks are ok)
- Consume > 3 drinks/day of any alcoholic beverage
- Smoker. (Former smokers must be smoke free for 6 months)
- You plan to move out of the study area within the next 3 months, or plan to be out of the study area for more than 1 week (~7 days) during the course of the study.

Number of Subjects

We will enroll 20 right handed men and women aged 21-65 y with a BMI of 20.0-40.0 kg/m².

Recruitment Methods

Traditional PBRC recruiting methods will be utilized by marketing and the recruiting core.

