Pulse oximeter: The pulse oximeter is an optical sensor that clips onto one of the fingers of either hand or toes of either foot. It shines a light through the skin to gather proxy measures of blood oxygenation while the scan is being collected. Dynamic MRI data, especially functional and perfusion MRI, is commonly corrected by regressing the time course of peripheral blood oxygenation out of the raw time series data acquired. The sensor attaches snugly to the finger but generally does not pinch or cut off the flow of blood.

Image and video display screen: Participants view images projected from a screen through a mirror mounted on the MRI head coil. Commonly deployed experimental paradigms display images during fMRI data collection to assess responses of the brain to various visual stimuli.

Headphones: MR-safe headphones are worn inside the head coil and over the ears.

Button boxes: In functional MRI experiments, participants are commonly asked to indicate responses to questions about the images, sounds, smells, and tastes exposed to them in the scanner by pressing buttons on button boxes placed in their hands.

MR scanning

The scanner technician runs a series of sequence acquisitions, each of which quantify a different aspect of tissue structure and function, or covers a slightly different portion of the anatomy. Each sequence acquisition emits a series of buzzing or grinding noises over the course of 1 to 10 minutes while data is acquired. Before each sequence acquisition, the technician communicates with the participant via a speaker and microphone inside the scanner bore; the participant is asked about his/her comfort and is reminded to lie perfectly still during the subsequent sequence acquisition. The technician has an unobstructed view of the participant to identify movement during acquisition or other signs of discomfort. After scanning, the participant is removed from the scanner tube and assisted out of the scanner suite.

Statistical analysis. The study will use an intent to treat approach. Following evaluation of data normality, a mixed model ANOVA will be used to test if change on the outcome variables differed between treatment and control across time. LS Means will also test if change from baseline was significantly different from 0. Fixed effects will include age and sex.

Power Analysis:

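### For fasted brain activation and the less repeatable questionnaires, the named model compares raw change between arms without the participant's own Week 0 value, which costs precision and leaves in chance baseline imbalance at 10 per arm (minor)

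*Protocol*

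**What the plan says.** The Statistical analysis paragraph gives one model for all outcome variables: "a mixed model ANOVA will be used to test if change on the outcome variables differed between treatment and control across time". It adds "LS Means will also test if change from baseline was significantly different from 0" and, on covariates, "Fixed effects will include age and sex". It names neither the Week 0 value of the outcome as a covariate nor any constraint on the arms' Week 0 means.

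On size, Inclusion and Exclusion Criteria sets a total of 20 participants. On allocation it says "10 participants will be randomized to the SSB and solid groups, respectively", and on stratification "Participants will be stratified based on sex and BMI class".

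Specific Aims makes brain activation a between-arm question: "Changes in brain activation will be measured and tested for differences among the groups". Table 1 places the questionnaires, behavioural tasks and fMRI at Week 0 and Week 4 only.

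The Week 0 visit contains both fasted and fed scans. Under Fasting vs. Fed Neural Activation Patterns, the participant eats the assigned food between the two, so the fasted scan precedes the first serving and the fed scan follows it. The Food Familiarity and Liking Procedure comes after all scanning is finished.

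**The concern.** Subtracting the Week 0 value assumes in effect that a unit difference at Week 0 persists as a full unit at Week 4. For a measure with modest repeatability it does not: a participant who is high at Week 0 tends to drift back. Raw change then adds noise from the Week 0 measurement. If one arm starts higher by chance, regression to the mean makes that arm appear to fall relative to the other.

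With 10 per arm, chance gaps of this kind are common. Stratification by sex and BMI class is not aimed at activation, cravings or appetite ratings. Two things are at stake: the between-arm estimate for brain activation, where the stated hypothesis is no difference and avoidable noise makes a null result easier to misread; and the estimates that Power Analysis says will feed future power calculations.

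**Working it through.** The protocol gives no SD, effect size or power, so there is no stated figure to reproduce.

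**Inputs from the protocol.** n = 10 per arm (N = 20); age and sex in the model; two assessments, Week 0 and Week 4.

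**Assumptions.** SD = 1 at both visits; complete pairs; Week 0 means free in the planned model; Week 0 to Week 4 correlation ρ not given, so ranged.

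**Formulas for the variance of the arm difference.**
- Raw change: 2(1 − ρ) × (2/n)
- With the Week 0 value as covariate: (1 − ρ²) × (2/n)
- Large-sample ratio, adjusted over raw change: (1 + ρ)/2

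**Small-sample cost of covariates.** With k covariates the variance is multiplied by 1 + k/(N − 3 − k).
- Age and sex (k = 2): 1 + 2/15 = 1.133, with 16 residual df.
- Plus the Week 0 value (k = 3): 1 + 3/14 = 1.214, with 15 residual df.
- The ratio at this sample size is therefore (1 + ρ)/2 × 1.214/1.133 = (1 + ρ)/2 × 1.071.

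Example at ρ = 0.5: raw change 2 × 0.5 × 0.2 × 1.133 = 0.227 (SE 0.476); adjusted 0.75 × 0.2 × 1.214 = 0.182 (SE 0.427); ratio 0.80.

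| ρ (assumed) | SE, raw change | SE, adjusted | Variance ratio | CI-width ratio | Carry-over from a 0.5 SD gap |
|---|---|---|---|---|---|
| 0.3 | 0.563 | 0.470 | 0.70 | 0.84 | 0.35 SD |
| 0.5 | 0.476 | 0.427 | 0.80 | 0.90 | 0.25 SD |
| 0.7 | 0.369 | 0.352 | 0.91 | 0.96 | 0.15 SD |
| 0.9 | 0.213 | 0.215 | 1.02 | 1.01 | 0.05 SD |
| 0.95 | 0.151 | 0.154 | 1.05 | 1.03 | 0.025 SD |
| 0.99 | 0.067 | 0.070 | 1.07 | 1.04 | 0.005 SD |

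The CI-width ratio also includes the change in t quantile from 2.1199 (16 df) to 2.1314 (15 df).

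**Break-even.** (1 + ρ)/2 × 1.071 = 1 gives ρ = 0.87 for the SE; allowing for the t quantile it is about 0.85 for CI width. Above that the extra covariate costs more than it gains.

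**Chance imbalance.** The between-arm Week 0 difference has SD √(2/10) = 0.447. P(|gap| > 0.5 SD) = 2[1 − Φ(0.5/0.447)] = 0.26. Given a gap d, raw change is shifted by −(1 − ρ)d, which is the last column of the table in absolute size.

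**Simulation check** (8,000 trials per ρ, 10 per arm, age and sex in both models). At ρ = 0.3, 0.5 and 0.7 the variance ratios were 0.69, 0.79 and 0.91. The slopes of the change estimate on the baseline gap were −0.71, −0.51 and −0.30, and about 0 after adjustment. Type I error was between 4.5% and 5.2% under both analyses, and the change estimate averaged about 0 over randomisations.

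**The case against.** **The covariate list is not closed.** The sentence says only that age and sex are included, does not even mention arm or time, and leaves open whether Week 0 means are free. An SAP that is not shown could add the Week 0 value or a common-mean constraint. That is fair, and it rules out saying that the protocol forbids adjustment. But the protocol does choose a change-based model and does name covariates, and nothing in it supplies the adjustment.

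**The gain depends on ρ, which is assumed.** This stands. The range is shown for that reason, and the more repeatable questionnaires may gain nothing.

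**Body composition.** A reader might infer that waist, hip and impedance lose precision too. The documents do not support that. Over four weeks in a sample described by "We will enroll 20 right handed men and women aged 21-65 y with a BMI of 20.0-40.0 kg/m²", ρ for body-size measures is probably above 0.85 to 0.87 (an assumption). Adjustment would then gain nothing and could add about 2% to 7% to the variance. Stratification by BMI class limits imbalance in body size further. The same holds for body weight.

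**The fed scan.** A reader might want the Week 0 fasted value as covariate for the Week 4 fed value. That would mix the acute effect of the serving just eaten into the arm contrast, whereas change between fed scans removes an acute effect that is stable over time. A common Week 0 mean is not justified either, because the Week 0 fed value already follows the assigned food. The Food Familiarity and Liking Procedure has the same difficulty.

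**Incomplete pairs.** The exact equality with a change-score analysis needs complete pairs. With dropouts or skipped items it is approximate.

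**Conclusion.** The point holds for a limited set of outcomes: fasted fMRI activation, and the less repeatable questionnaires and tasks completed before the first assigned serving. For these the named analysis amounts to a change-score comparison. At assumed ρ of 0.3 to 0.7, adding the Week 0 value would cut the variance of the arm difference by about 30% to 9% and CI width by about 16% to 4%. It would also remove the carry-over of chance imbalance.

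A reader might infer that the planned test is invalid or the primary endpoints compromised. Neither follows. Type I error stays near 5% and the change estimate is unbiased over randomisations; the bias is conditional on an observed gap. Study Endpoints names feasibility and change in body weight as primary. Feasibility is not involved, and body weight is expected to gain nothing from adjustment. The study is also an unpowered pilot. Severity is minor.

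The conclusion rests on equal SDs at the two visits, complete pairs, free Week 0 means and the assumed range of ρ.

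**What to change.** Add to the Statistical analysis paragraph that, for fasted fMRI activation and for questionnaires and behavioural tasks completed before the first assigned serving, the between-arm model includes the participant's Week 0 value of that outcome along with arm, age and sex. The response may be change or the Week 4 value; the arm estimate is the same. Using change keeps the planned LS Means test against 0. Alternatively, keep the two-visit mixed model and constrain both arms to a common Week 0 mean for these outcomes. The Week 0 visit list puts the questionnaires ahead of the scans and the serving but does not say that this is the order followed; the sentence should state it.

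Leave body weight, waist, hip and impedance as change. Keep the planned change analysis for the fed scan and the Food Familiarity and Liking Procedure, with no common Week 0 mean.

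Cost: a short addition to the text, no new data, at most one residual degree of freedom (16 to 15), and a small variance penalty for any outcome whose ρ turns out above about 0.85.

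### Do the reference to a control arm that does not exist, and the within-arm tests against zero, undermine the weight and fMRI analyses?

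*Protocol*

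**What the plan says.** Under Study Endpoints the design is stated as follows: "A randomized parallel arm design trial examining solid sugar vs. SSB treatments will be performed". The inclusion section adds that "10 participants will be randomized to the SSB and solid groups, respectively", and both foods supply 240 kcal/day. No arm is untreated, non-caloric or on usual diet alone.

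Aim 2 carries two weight hypotheses. Between arms: "The SSB group will have no difference in change in body weight compared to the solid group (between group effects". Within arms: "The SSB and solid groups will have increased weight compared to baseline (within group effects". A separate paragraph below Aim 2 predicts that activation in reward areas will change from baseline in both arms, with no difference between them.

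The Statistical analysis section specifies a mixed model to "test if change on the outcome variables differed between treatment and control across time" and then says that "LS Means will also test if change from baseline was significantly different from 0". The exclusion list defines weight instability as "more than 10 lbs. weight gain or loss in last 6 months", so smaller changes in either direction are allowed. Body weight and feasibility are the primary endpoints.

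**The concern.** Two things catch the eye. First, the sentence defining the between-arm test speaks of change that "differed between treatment and control across time", yet neither arm is a control. Taken literally, the comparison could not be run, and a reader might suppose that a sugar-free comparator exists.

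Second, the predicted weight gain in both arms can be examined only by before-after change. Randomisation assigns food form, not whether sugar is given, so nothing in the design separates the food from whatever the participants' weight was already doing. The entry rule tolerates drift that looks large beside any plausible effect. The fMRI prediction has a similar weakness, because the image task is performed at baseline and again at follow-up, so repeated exposure is a rival explanation for change.

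The stake is interpretation. A significant within-arm change might be reported as caused by the food and carried into the larger grant that the Power Analysis section has in view.

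**Working it through.** The protocol gives no effect size, SD, alpha or power, so it has no figure of its own to reproduce. The check has five steps.

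**1. What the between-arm test can mean.** There are two arms, 10 participants each. One contrast is possible: mean change on SSB minus mean change on solid. Replacing treatment and control by the arm names leaves the model, the estimate, the interval and the p-value as they were.

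**2. Whether drift biases that contrast.** Let *d* be mean drift common to both arms and *f* the food effect. Then (*d* + *f*SSB) − (*d* + *f*solid) = *f*SSB − *f*solid. Common drift cancels. The Background section gives the study's purpose as exactly this question: whether food form makes weight change differ.

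**3. How large permitted drift could be.**
- Entry limit: 10 lb in 6 months. Over four weeks, 10 × 4/26 = 1.54 lb; × 0.4536 = 0.70 kg.
- Gain with no compensation: 240 × 28 = 6,720 kcal; / 7,700 kcal/kg = 0.87 kg. The energy density is an assumption; 9,400 to 7,000 kcal/kg gives 0.71 to 0.96 kg.
- Ratio: 0.70/0.87 = 80% (73% to 98% over that range).

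This sets one person's maximum against a group-mean effect. An arm mean of 0.70 kg would need all 10 participants at the limit, in the same direction, and continuing at that pace after entry. The rule admits losses as readily as gains.

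**4. What drift does to the test against zero.** Assume a two-sided 5% one-sample t-test with n = 10 as an approximation to the LS-mean test, no food effect, and an SD of four-week change of 0.7, 1.0 or 1.5 kg. The noncentrality is drift × √10 / SD on 9 degrees of freedom. The chance of rejecting is:

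| Mean drift in the arm | SD 0.7 kg | SD 1.0 kg | SD 1.5 kg |
|---|---|---|---|
| 0 kg | 5% | 5% | 5% |
| 0.20 kg | 13% | 9% | 7% |
| 0.35 kg | 29% | 17% | 10% |
| 0.70 kg | 80% | 51% | 26% |

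The protocol gives no reason to expect a non-zero mean drift. Where drift is present, a rejection is still a correct statement that weight changed from baseline; only a causal reading would be wrong. Because a 95% interval excludes zero exactly when the two-sided 5% test rejects, reporting intervals in place of tests would convey the same information.

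**5. Whether the obvious additions help.**
- *Screening-to-Week-0 weight as a drift check.* The gap is about 7 days, so even ceiling drift is 0.70 × 7/28 = 0.17 kg. With 10 people and an SD of 0.7 kg (assumed), the standard error is 0.7/√10 = 0.22 kg, larger than the quantity sought. The Study Timelines section ties Week 0 to the self-reported luteal phase in women but gives no such timing for screening, so the check could confuse menstrual-phase weight change with drift.
- *A multiplicity figure for fMRI.* Six food-versus-control-image contrasts, two states and two arms make 24 tests, and 1 − 0.95^24 = 71%. The protocol does not name those contrasts. It allows up to seven image categories, with control images optional. Independence is implausible when contrasts share images and participants. Multiplicity is also a different matter from the lack of a control arm, and one that a SAP commonly settles.

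**The case for a change.** The best case for amending is that body weight is a primary endpoint, that one of its two hypotheses has no concurrent comparator, and that the words within group effects invite a causal reading. Correcting the label and calling the within-arm results descriptive would cost a few words. For fMRI the case is, if anything, stronger: before the Week 4 scan participants have done the task fasted and fed, and have rated its images once, so familiarity alone might shift activation.

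Part of this stands. The word control is wrong, and a before-after change in either arm cannot be credited to the food. But the within and between labels on the weight hypotheses can be read as ordinary analysis-of-variance vocabulary, and the within label is not attached to the fMRI paragraph at all. The imaging element of Aim 1 is to show that scans can be acquired and analysed. The protocol does not say whether the Week 4 image set is identical to that at Week 0, and it gives no basis for sizing habituation. The feared causal claim is a prediction about a future report; the plan does not make it.

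**Conclusion.** No change is needed. The reference to a control is a clerical slip with only one possible reading, SSB versus solid, and correcting it alters no result. The within-arm tests match the hypothesis they serve, and the randomised contrast answers the study's stated question free of drift common to both arms.

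The 0.70 kg figure is a ceiling for one participant under an assumed steady continuation; comparing it with 0.87 kg also assumes 7,700 kcal/kg. Neither measures the error of the planned test, which stays at its nominal level (5% if alpha is 0.05) when mean drift is zero. What remains is a caution for whoever reports the trial: four-week change within an arm is descriptive. In a pilot of 20 without a power calculation, that is ordinary good reporting and not a defect of the plan.
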